### **3.2 Primary Study Endpoints**

This phase I/IIa study is designed to test the safety and relative engraftment of the autologous T cells transduced with the anti-CD19 lentiviral vector in patients with relapsed, refractory and incurable CD19+ B cell malignancies.

Primary safety, feasibility and engraftment endpoints include:

1. Occurrence of study related adverse events, defined as NCI CTC  $\geq$  grade 3 signs/symptoms, laboratory toxicities and clinical events that are possible, likely or definitely related to study treatment at any time from the infusion until week 24. This will include infusional toxicity and any toxicity possibly related to the CART-19 cells including but not limited to:
  - a. Fevers
  - b. Capillary leak
  - c. Rash
  - d. Neutropenia, thrombocytopenia, anemia, marrow aplasia
  - e. Hepatic dysfunction
  - f. Pulmonary infiltrates or other pulmonary toxicity
  - g. Hypotension
  - h. In the allo cohort only, GVHD
2. Feasibility to manufacture CART-19 cells from patient apheresis products. The number of manufactured products that do not meet release criteria for vector transduction efficiency,

CONFIDENTIAL

T cell purity, viability, sterility and tumor contamination will be determined (defined as “manufacturing failures”).

3. Duration of *in vivo* survival of CART-19 cells is defined as “engraftment”. The primary engraftment endpoint is the # DNA vector copies per ml blood of CART-19 cells on week 4 after the first infusion. Q-PCR for CART-19 vector sequences will also be performed after each infusion, weekly x 4, monthly x 6, and every 3 months thereafter until any 2 sequential tests are negative documenting loss of CART-19 cells.
4. New onset secondary malignancies.

### **3.3 Secondary Study Endpoints**

Secondary endpoints include:

1. Describe anti-tumor responses to CART-19 cell infusions.
  - a. For subjects with active disease, typical response criteria for partial response (PR) or complete response (CR) will be determined. Response determination will be only “descriptive” given the small number of subjects to be treated. The main endpoint for efficacy is Day 28 overall response rate. Other endpoints, including duration of remission, best overall response, CR/CRi with MRD negative bone marrow, RFS and EFS may also be summarized.
  - b. For subjects treated with MRD (identified by PCR analysis of blood or marrow), determine elimination of MRD scored as yes/no.
  - c. For subjects treated in remission, describe progression-free survival (PFS).
2. Describe overall survival and cause of death
3. For patients with stored or accessible tumor cells (such as patients with active CLL or ALL) determine if *in vitro* cell killing assays of CART-19 cells against patient tumor correlates with clinical response.
4. Determine if host immunity develops against the murine anti-CD19 or other elements of the transgene or vector such as VSV-G, and assess correlation with loss of detectable CART-19 (loss of engraftment).
5. In subjects infused with mixtures of CART-19 TCR $\zeta$  and TCR $\zeta$ :4-1BB cells, RT-PCR analysis of whole blood will be used to detect and quantify relative survival of CART-19 TCR $\zeta$  and TCR $\zeta$ :4-1BB cells over time.
6. Determine the relative subsets of CART-19 T cells (Tcm, Tem, and Treg)

### **3.4 Exploratory Study Endpoints**

Exploratory endpoints include:

1. Describe the correlation of test expansion results with manufacturing feasibility and clinical outcome.

## **4 SUBJECT SELECTION AND WITHDRAWAL**

### **4.1 Inclusion Criteria**

Inclusion criteria are designed to include a broad spectrum of subjects with documented CD19+ hematologic malignancies. Enrollment at CHOP will largely be limited to ALL and high-grade B cell NHL. Male and female subjects with CD19+ B cell malignancies in patients with no available curative treatment options (such as autologous or allogeneic SCT) who have limited

CONFIDENTIAL

prognosis (several months to <2 year survival) with currently available therapies will be enrolled:

1. Eligible diseases: CD19+ leukemia or lymphoma
  - a. ALL without curative options for therapy, including those not eligible for allogeneic SCT because of:
    - age
    - comorbid disease
    - other contraindications to TBI-based conditioning (required for ALL SCT)
    - lack of suitable donor
    - prior SCT
    - Declines allo SCT (in CR3) as a therapeutic option after documented discussion about the role of SCT with a BMT physician not part of the study team (see note below).
  - Patient may be in any complete response, or patient may have active disease but responding or stable after most recent therapy (see 5.2 Patient Eligibility to Receive CART-19 Transduced T Cells, below). The intent is not to enroll patients with no degree of disease control, or rapidly increasing disease burden between enrollment and cell infusion.
  - b. Follicular lymphoma, previously identified as CD19+
    - At least 2 prior combination chemotherapy regimens (not including single agent monoclonal antibody (Rituxan) therapy).
    - Stage III-IV disease.
    - Less than 1 year between last chemotherapy and progression (i.e. most recent progression free interval <1 year).
    - Disease responding or stable after most recent therapy (chemotherapy, MoAb).
  - c. CLL
    - At least 2 prior chemotherapy regimens (not including single agent monoclonal antibody (Rituxan) therapy).
    - Less than 1 year between last chemotherapy and progression (i.e. most recent progression free interval <1 year).
    - Not eligible or appropriate for conventional allogeneic SCT.
    - Disease responding or stable after most recent therapy (chemotherapy, MoAb)
  - d. Mantle cell lymphoma
    - Beyond 1st CR with relapsed or persistent disease and not eligible or appropriate for conventional allogeneic or autologous SCT.
    - Disease responding or stable after most recent therapy (chemotherapy, MoAb).
    - Relapsed after prior autologous SCT.
  - e. B-cell prolymphocytic leukemia (PLL) with relapsed or residual disease after at least 1 prior therapy and not eligible for allogeneic SCT.
  - f. Diffuse large cell lymphoma or other high-grade NHL, previously identified as CD19+
    - Residual disease after primary therapy and not eligible for autologous SCT.
    - Relapsed after prior autologous SCT.
    - Beyond 1st CR with relapsed or persistent disease and not eligible or appropriate for conventional allogeneic or autologous SCT.
2. Age 1 to 24 years. Patients ages 22-24 will only be enrolled if they are currently being treated at CHOP or another pediatric facility/oncologist.

CONFIDENTIAL

3. Expected survival > 12 weeks
4. Creatinine < 2.5 mg/dl and less than 2.5x normal for age
5. ALT ≤ 5x normal
6. Bilirubin <2.0 mg/dl
7. Any relapse after prior SCT will make patient eligible regardless of other prior therapy.
8. Patients with relapsed disease after prior allogeneic SCT (myeloablative or non-myeloablative) will be eligible if they meet all other inclusion criteria and
  - a. Have no active GVHD and require no immunosuppression
  - b. Are more than 4 months from transplant (6 months at infusion; see Section 5.2)
9. For those patients who require leukapheresis for T cell collection (i.e. no previously collected product exists), adequate venous access for apheresis or eligible for appropriate catheter placement, and no other contraindications for leukapheresis.
10. Voluntary informed consent is given.
11. Patients with CNS3 disease will be eligible if CNS disease is responsive to therapy (at infusion, must meet criteria in Section 5.2) (see section 15.5 for definitions of CNS1, CNS2 and CNS3 disease)

NOTE on 1.a.vi – declines SCT: SCT is performed in patients with ALL in CR3, but the outcomes are problematic. Most data suggest about a 30% OS in the highly selected group of patients. A report which places this in context was published in JCO by Saarinen-Pihkala et al., looking at the overall (population-based) experience in CR3 ALL. Of 71 pts with ALL in CR3, OS after SCT was 30% and EFS 15%. Overall EFS of the 71 patients in CR3 was 7%. These numbers indicate that a decision to pursue a therapy other than SCT in CR3 ALL is rational, and that CART-19 therapy may offer a benefit to patients in this group.

#### **4.2 Exclusion Criteria**

1. Pregnant or lactating women. The safety of this therapy on unborn children is not known. Female study participants of reproductive potential must have a negative serum or urine pregnancy test performed within 48 hours before infusion.
2. Uncontrolled active infection.
3. Active hepatitis B or hepatitis C infection.
4. Concurrent use of systemic steroids at the time of cell infusion or cell collection, or a condition, in the treating physician's opinion, that is likely to require steroid therapy during collection or after infusion. Steroids for disease treatment at times other than cell collection or at the time of infusion are permitted. Use of inhaled steroids, or hydrocortisone for physiological replacement in patients with adrenal insufficiency are permitted as well.
5. ~~Presence of grade 2-4 acute or extensive chronic GVHD. See section 15.2 for definition of chronic GVHD. (NO LONGER APPLICABLE- Retired from V14)~~
6. ~~Under treatment for GVHD. (NO LONGER APPLICABLE- Retired from V14)~~
7. Previous treatment with any gene therapy products.
8. ~~Feasibility assessment during screening shows insufficient expansion in response to CD3/CD28 costimulation. (NO LONGER APPLICABLE – Retired from V11)~~
9. Any uncontrolled active medical disorder that would preclude participation as outlined.
10. HIV infection.

CONFIDENTIAL

11. [REDACTED]
12. CNS3 disease that is progressive on therapy, or with CNS parenchymal lesions that might increase the risk of CNS toxicity
13. Acute or chronic GVHD requiring systemic therapy (topical allowed).

#### **4.3 Subject Recruitment and Screening**

Subjects will be identified through the clinical practices of the investigator or sub-investigators and through referrals from outside hospitals and physicians. No direct-to-patient advertising will be performed. The investigators will identify patients potentially meeting the study eligibility criteria through medical record reviews and the results of tests performed as part of routine clinical care. Subjects who are determined to be potentially eligible will be informed about the study. If the subject indicates willingness to participate in the study, the consent process will begin. Although many screening/eligibility tests are done routinely as part of standard oncology care, some are not, and written informed consent will be obtained before any non-SOC screening tests are conducted for research purposes. After informed consent has been obtained, the subjects will be evaluated for eligibility to ensure all inclusion and exclusion criteria are met. Eligible subjects will then be assigned a subject ID and considered enrolled by the sponsor. The test expansion (performed for exploratory purposes) will also occur in this phase. If and when the patient is eligible and enrolled with the sponsor, pheresis will occur if needed, and cell manufacturing begun.

The test expansion has been used to determine whether the subjects have an adequate number of T cells that can be successfully expanded with the anti-CD19 lentivirus vector, as determined from a sample of PBMC obtained by phlebotomy or prior apheresis at the first screening visit (~week -8).

Staggered enrollment on the CNS3 cohort: infusion of any subsequent patient on the CNS3 cohort will be delayed until 21 days after the prior CNS3 patient's infusion to allow for toxicity monitoring.

Female subjects of reproductive potential (women who have reached menarche or women who have not been post-menopausal for at least 24 consecutive months, i.e., who have had menses within the preceding 24 months, or have not undergone a sterilization procedure [hysterectomy or bilateral oophorectomy], or are not <11 years of age or who are not Tanner 1,) must have a negative serum or urine pregnancy test performed within 48 hours prior to entry.

Due to the high risk level of this study, while enrolled, all subjects must agree not to participate in a conception process (e.g., active attempt to become pregnant or to impregnate, sperm donation, in vitro fertilization). Additionally, if participating in sexual activity that could lead to pregnancy, the study subject must agree to use reliable and double barrier methods of contraception during the follow-up period of the protocol.

Acceptable birth control includes a combination of two of the following methods:

- Condoms\* (male or female) with or without a spermicidal agent.
- Diaphragm or cervical cap with spermicide
- Intrauterine device (IUD)
- Hormonal-based contraception

CONFIDENTIAL

Subjects who are not of reproductive potential (girls < 11 years of age or who are Tanner 1, women who have been post menopausal for at least 24 consecutive months or have undergone hysterectomy, salpingotomy, and/or bilateral oophorectomy or men who have documented azoospermia) are eligible without requiring the use of contraception. Acceptable documentation includes written or oral documentation communicated by clinician or clinician's staff of one of the following:

- Demographics show age < 11
- PE indicates Tanner 1 female
- Physician report/letter
- Operative report or other source documentation in the subject record (a laboratory report of azoospermia is required to document successful vasectomy)
- Discharge summary
- Laboratory report of azoospermia
- Follicle stimulating hormone measurement elevated into the menopausal range

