### **5.2 Patient Eligibility to Receive CART-19 Transduced T Cells**

- Disease response:

[figure not shown]
CONFIDENTIAL

- No evidence of high disease burden, that would, in the opinion of the treating physician, put the patient at significant potential risk for tumor lysis syndrome.
- Failure to maintain performance status as indicated in initial eligibility criteria
- If s/p allogeneic transplant, 6 months from transplant.
- Patients experiencing toxicities from their preceding cytoreductive chemotherapy will have their infusion schedule delayed until these toxicities have resolved. The specific toxicities warranting delay of T cell infusions include:
  - Pulmonary: Requirement for supplemental oxygen to keep saturation greater than 95% or presence of radiographic abnormalities on chest x-ray that are progressive
  - Cardiac: New cardiac arrhythmia not controlled with medical management
  - Hypotension requiring pressor support
  - Active Infection: Positive blood cultures for bacteria, fungus, or virus within 48 hours.

CNS3 cohort infusion criteria:

- 1) Disease status:
  - a. If CNS3 by spinal fluid involvement, stable/responding disease as indicated by:
    - i. stable or decreasing CSF WBC, and
    - ii. total CSF WBC < 100 in a sample obtained within 72 hours of CART-19 infusion.
  - b. If CNS3 by MRI findings, there must be interval stability or improvement on MRI within 2 weeks of infusion
  - c. If CNS3 by cranial nerve findings, there must be stability or improvement of these cranial nerve findings on exam post intervention
- 2) At least 21 days since any prior CNS3 patient was infused.
- 3) Patients with CNS3 disease requiring radiation therapy must be at least 8 weeks post radiation at CART-19 infusion
- 4) Patients must have no acute/ongoing neurologic toxicity > Grade 1 with the exception of a history of controlled seizures or fixed neurologic deficits that have been stable/improving over the past 3 months

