#### **8.4.1 Criteria for stopping or pausing the study**

The study will be stopped if:

- Any subject develops uncontrolled T cell proliferation that does not respond to management.
- The Investigator, Study Funder, Sponsor, DSMB, ACC DSMC, or any independent review board or regulatory body decides for any reason that subject safety may be compromised by continuing the study.
- The Sponsor or Study Funder decides to discontinue the development of the intervention to be used in this study.

The protocol will be paused pending submission of protocol pause to the FDA and review by the IRB and DSMB if any patient experiences any of the following events within two weeks of the CART-19 infusion:

- Life-threatening (grade 4) toxicity attributable to protocol therapy that is unmanageable, unexpected, unrelated to chemotherapy, and attributable to protocol therapy. This includes grade 4 GVHD. In terms of expected toxicity, we expect high fevers, hypotension, possible ICU admission and even mechanical ventilation. CRS and MAS can result in grade 4 liver toxicity, nephrotoxicity and other organ involvement. In addition, we have seen reversible confusion in 3 patients which fully resolved spontaneously over 2-4 days without treatment or sequelae.
- Death.
- If the V $\beta$  analysis pattern of insertion is found to favor a single dominant insertion site pattern the clinical trial will be placed on hold for dosing to allow evaluation of the subject in consultation with gene therapy experts, study investigators, DSMB, FDA and NIH.

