#### **8.4.2 Stopping rules related to the CNS3 cohort**

Accrual to the CNS3 cohort will be stopped for review if:

- 1) Any subject develops a grade 5 neurological toxicity attributable to CART-19 infusion.
- 2) Any subject develops grade 3/4 neurotoxicity or agitation, confusion, delirium, or psychosis (psychiatric) toxicity that has not resolved to  $\leq$  Grade 2 within 4 weeks with or without medical intervention (ie: anti-epileptics).
- 3) Any non-resolving grade 3 or 4 neuro toxicity or death due to neuro/psychiatric toxicity clearly attributable to the CART cells will lead to a hold on any further CNS3 patients enrolled in this high risk stratum pending subsequent review.

CONFIDENTIAL

Note on attribution: Toxicity is attributable to CART-19 infusion if, in the opinion of the principal investigator or sponsor, the event was more likely than not to be caused by the CART-19 cells. In making this determination, the investigator will assess:

- Timing (most other toxicities, other than cytopenias and hypogammaglobulinemia are resolved within 28 days of infusion).
- Predisposing structural CNS lesions, prior strokes, or prior seizure history
- Neurologic baseline at study entry
- Events during CRS that may have been predisposing to CNS toxicity (such as significant coagulopathy)
- Infections are most likely attributable to cytopenias due to disease and chemotherapy, and are therefore less likely to be due to CART-19 infusion

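### The 21-day CNS3 stagger ends before the 4-week neurotoxicity rule can be met, and no infusion criterion in section 5.2 asks whether the prior CNS3 patient's grade 3/4 event is still open

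*Combined protocol and SAP*

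**What the plan says.** Section 4.3 provides that "infusion of any subsequent patient on the CNS3 cohort will be delayed until 21 days after the prior CNS3" patient's infusion, and gives toxicity monitoring as the reason. The CNS3 infusion criteria in section 5.2 repeat this as item 2: "At least 21 days since any prior CNS3 patient was infused". The other three items are disease status, time since radiation and current neurological condition ("Patients must have no acute/ongoing neurologic toxicity > Grade 1", with exceptions for controlled seizures and stable deficits). All three describe the patient about to be infused.

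Section 8.4.2 opens with "Accrual to the CNS3 cohort will be stopped for review if" and lists three rules:

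- Item 1: a grade 5 neurological toxicity attributable to the cells.
- Item 2: a grade 3/4 neurological or listed psychiatric toxicity that has not come down to at most "Grade 2 within 4 weeks with or without medical intervention".
- Item 3: a grade 3 or 4 neurotoxicity described as non-resolving, or a neurological or psychiatric death, that is clearly attributable to the cells. This leads to a "hold on any further CNS3 patients enrolled in this high risk stratum pending subsequent review".

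Section 8.4.1 pauses the whole protocol "if any patient experiences any of the following events within two weeks of the CART-19 infusion". The events are death, grade 4 toxicity that is unmanageable, unexpected and attributable, and a dominant insertion-site pattern. The grade 4 bullet also records that "we have seen reversible confusion in 3 patients which fully resolved spontaneously over 2-4 days".

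**The concern.** A stagger lets the outcome in one patient inform the decision to treat the next. Here the waiting period is shorter than the time the protocol allows before it calls a grade 3/4 neurological event persistent. The only infusion criterion that refers to the prior patient counts days and does not ask about that patient's condition. A site that follows the text exactly could infuse a second child with CNS3 disease while the first child's grade 3/4 event is unresolved and its outcome unknown. Safety in CNS3 disease is secondary objective 6, and section 8.4.2 itself treats these patients as high risk. What is at stake is patient safety in this cohort, not a primary endpoint or an analysis.

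**Working it through.** The plan gives no figure to reproduce. The check is day arithmetic and a reading of each rule that could hold the next infusion.

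**Inputs**
- Stagger: 21 days (4.3; 5.2, CNS3 item 2).
- Resolution window: 4 weeks = 28 days (8.4.2, item 2). The start of this clock is not stated.
- Dose days: Day 0; the second dose on day 1, or up to day 4 (6.6); a possible further dose on day 14 or later (Study Summary; 15.1). The dose that starts the 21 days is not stated.
- Onset: days 1 to 14 is an assumed illustrative range. Day 21 is added because section 5.1 places later toxicities at 7 to 21 days after infusion. That sentence concerns cytokine release and possibly tumor lysis, so applying it to neurotoxicity is also an assumption.

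**Formulas**
- Next permitted CNS3 infusion = a + 21, where a is the day of the dose that starts the stagger.
- Earliest day item 2 can be met = 28 if the clock starts at Day 0, or t + 28 if it starts at onset on day t.
- Gap = earliest item 2 day minus next permitted infusion day.

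| Stagger starts on day (a) | Next infusion on day | Gap, clock from Day 0 | Gap, onset day 1 | Onset day 7 | Onset day 14 | Onset day 21 |
|---|---|---|---|---|---|---|
| 0 | 21 | 28 − 21 = 7 | 29 − 21 = 8 | 35 − 21 = 14 | 42 − 21 = 21 | 49 − 21 = 28 |
| 4 | 25 | 28 − 25 = 3 | 29 − 25 = 4 | 35 − 25 = 10 | 42 − 25 = 17 | 49 − 25 = 24 |
| 14 | 35 | 28 − 35 = −7 | 29 − 35 = −6 | 35 − 35 = 0 | 42 − 35 = 7 | 49 − 35 = 14 |

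Zero or a negative value means no gap. If both clocks start at the same dose, the gap is 28 − 21 = 7 days whichever dose that is.

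With infusions at minimum spacing from Day 0 (days 21, 42, ...), one further CNS3 patient could be infused before item 2 can be met for onset up to day 14. For onset on day 21 it is two, because days 21 and 42 both precede day 49.

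**Could another rule hold the infusion first?**
- 8.4.2 item 1 needs a grade 5 event.
- 8.4.2 item 3 covers grade 3 and has no two-week limit. But it gives no time after which an event counts as non-resolving, it requires clear attribution, and the section 5.2 infusion check does not refer to it.
- The toxicity arm of the 8.4.1 pause needs grade 4, so a grade 3 event never meets it. It also needs the event to be unexpected and unmanageable and to occur within two weeks, so onset on days 15 to 21 falls outside.
- The data and safety monitoring committee reporting duties (8.3.3) and the discretionary stop (8.4.1) do not require a hold.

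A persisting grade 3 event, or a grade 4 event with onset after two weeks, can therefore reach day 21 without a required hold unless item 3 is read broadly.

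**The case against.** The strongest reply rests on item 3 of 8.4.2. It is mandatory and covers grade 3, and because it sets no time limit it need not wait 4 weeks. If it did wait, it would largely repeat item 2. On that reading, an attributable event that is still open and not improving on day 21 already holds the next patient. The lead paragraph of 8.4 also allows a stop for unexpected serious events related to the cells, with no two-week limit. Neurotoxicity lasting 7 to 14 days could well be judged unexpected against confusion that cleared in 2 to 4 days. Serious events go to the sponsor within 24 hours, and an unexpected grade 4 event triggers a team discussion within 24 business hours, so a next infusion given without thought is unlikely. Finally, the stagger and item 2 do different jobs, and nothing says one must outlast the other.

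Much of this stands. It is a gap between two rules, not a contradiction, and item 3 may close part of it. Events of uncertain attribution, and events judged to be slowly improving, remain. For those, the protective steps are matters of judgement or reporting. The DSMB charter was not available, so any CNS3 review it contains could not be assessed. Reported confusion was short, so the gap matters only for prolonged events. That experience cannot settle the risk in a cohort the protocol treats as a separate high-risk group.

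**Conclusion.** The concern holds. With the stagger counted from the initial doses (days 0 to 4), the next CNS3 infusion is allowed on days 21 to 25. That is 3 to 7 days before item 2 can be met if its clock starts at Day 0, and 4 to 21 days before if it starts at an onset on days 1 to 14. If a day-14 dose restarts the stagger, there is no gap when the item 2 clock runs from Day 0 or from an onset by day 7, and a 7-day gap for onset on day 14. These are ranges because neither the anchor dose nor the clock start is stated, and the onset days are assumptions. That no CNS3 criterion in 5.2 asks about the prior patient's toxicity does not depend on them.

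This should be fixed as a safety matter. It will rarely apply: an event that began on day 7 or 14 and is still open on day 21 has lasted 14 or 7 days, against the 2 to 4 days reported in 8.4.1.

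**What to change.** Keep the 21-day minimum; it need not be lengthened for everyone. Then:

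1. In 4.3 and the CNS3 criteria of 5.2, add that no CNS3 patient is infused while any prior CNS3 patient has a grade 3/4 neurological or psychiatric toxicity that is not attributed to another cause and has not resolved to grade 2 or lower. The hold ends when the event resolves or the 8.4.2 review is complete.
2. In 8.4.2, state that an invoked rule holds infusion of CNS3 patients already enrolled as well as new accrual. Section 7.1 gives about 6 to 8 weeks from screening and apheresis to dosing, so patients may be enrolled and waiting when a rule is met.
3. For clarity, state which dose starts the 21 days and which date starts the 4 weeks.

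The cost is wording in three sections, with no extra patients, visits or tests. A CNS3 infusion may be delayed while such an event is open, and the waiting patient's disease could progress in that time. On the experience reported in 8.4.1, such a hold would rarely be in force at day 21.
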